## 10.3.2 Sample Size

Power for the primary outcome of rate of change in MDS-UPDRS I-III total score is based on a random slopes model with shared baseline. The model will include fixed effects of time, treatment x time, gender, gender x time, an indicator of baseline MAO-B inhibitor use, and baseline MAO-B inhibitor use x time and random site- and subject-specific intercepts and slopes, each with unstructured covariance. MDS-UPDRS assessments completed after a subject has initiated dopaminergic therapy will be censored.

Based on applying the same primary analysis model to data from SURE-PD, the following variance components were estimated for UPDRS I-III total scores: site-level variance (intercept = 9.75, slope = 0.0123 / month, covariance = -0.346), subject-level variance (intercept = 77.4, slope = 0.230 / month, covariance =2.87), and residual variance = 13.9. We assume that 70% of subjects will initiate dopaminergic therapy based on experience in SURE-PD plus up to 8% additional lost to follow-up prior to initiating dopaminergic therapy. With the planned schedule for MDS-UPDRS assessments (screening, baseline, 3 weeks, 6 weeks, 12 weeks, and then quarterly through 24 months), the variance and censoring estimates above imply an effective standard deviation for UPDRS I-III total score slopes of 0.587 units / month or 0.758 units / month on the scale of MDS-UPDRS I-III total scores.

Given a standard deviation of 0.76 units / month, a final two-sided test at alpha = 0.046 allowing conservatively for two interim analyses at alpha = 0.001 each, the study would have 80% power with n = 270 subjects randomized 1:1 to placebo or urate elevation if the true effect of treatment were to reduce the rate of increase in MDS-UPDRS I-III total score by 6.3 points over 2 years.

This estimate of power is robust to variable gender-specific enrollment rates and treatment efficacy as long as the average effect of treatment across genders in the ratio enrolled is 6.3 points over 2 years (Fig. 14A). If urate elevation reduces the average rate of progression by 6.3 points over 2 years only among male or female participants and the other gender experiences less benefit, power would be lower (Fig. 14B). This is unavoidable if a large proportion of the enrolled population accrues less benefit from the intervention. Conversely, power would be greater than 80% if one gender experiences a benefit greater than 6.3 points over 2 years and the other gender experiences at least that large a benefit.

[figure not shown]

Figure 14. (A) Power for the primary aim across a range of gender-specific treatment responses, all cases with the average treatment response across genders equal to the MCID of 6.3 points over 2 years. Note that equal prevalence of male (M) and female (F) participants is plotted, but the power curve for other prevalence ratios are so similar as

to be indistinguishable at this scale. (**B**) Power for the primary aim when the effect of treatment on one gender is equal to the MCID and the effect on the alternate gender varies from 50% to 150% of MCID for a range of different prevalence ratios.

## 10.3.3 Secondary Outcomes

The trial will have an 80% probability of observing at least one instance of any class of adverse event expected to occur in at least 1.2% of individuals receiving inosine. The trial will have 80% power to detect increased risk of any class of adverse event among subjects receiving inosine if the true risk is two-fold higher and the expected proportion among placebo subjects is at least 14% or if the true risk if four-fold higher and the expected proportion among placebo subjects is at least 3.4%. The trial has 80% probability of declaring serum urate elevation tolerable if the true proportion tolerant under the definition given in Sec. 10.2.2.2 at 12 weeks and 24 months is at least 62%.

The estimated SE for symptomatic effects on UPDRS I-III total scores during wash-in between the moderate elevation and placebo arms in the SURE-PD trial was 0.53 units / month. With n=25 subjects per treatment group in SURE-PD, the expected SE for estimating symptomatic effects in this trial will be roughly sqrt (25/135) \* 0.53 = 0.23 units / month. With that SE, the trial would have 80% power to detect symptomatic effects on the order of a difference in slopes during wash-in or wash-out of 0.65 units/month.

The Kaplan-Meier product-limit estimate from the SURE-PD trial of the proportion of placebo subjects requiring dopaminergic therapy by 24 months was 62%. Assuming constant hazard at the same rate among placebo subjects in this trial during period 1 (0 to 24 months) and 8% loss to follow-up prior to determining need for dopaminergic therapy, the trial will have 80% power to detect a hazard ratio of 0.62. Extrapolating to 27 months, we expect a total of 67% of placebo arm subjects to have disability warranting dopaminergic therapy at the end of period 2 (24 to 27 months). The study would have 80% power to detect a difference in the proportion of subjects with disability warranting dopaminergic therapy if 50% or fewer of active arm subjects have progressed by the end of the trial.

Given preliminary data from SURE-PD on the variance components from random-slope models for MoCA after Rasch score conversion and S&E ADL, the effective standard deviations (in points per month) for these measures given our planned follow-up schedule are 0.038 and 0.31, respectively. Weaver et al. report an among-person standard deviation for PDQ-39 at 24 months after deep brain stimulation of 14.2 to 15.3. Assuming conservatively no within-person covariance, that would imply a standard deviation for 24-month change of approximately 30. Given these estimates, the trial will have 80% power to detect 2-year treatment differences on these outcomes as small as 0.31, 2.5, and 10.3, respectively.

## 10.4 Data Monitoring

In addition to periodic review of accrual and adverse events by an independent DSMB to evaluate feasibility and safety, the trial will utilize an information-based group-sequential design with plans for two non-binding interim analyses for evaluating efficacy, futility, and sample size requirement.

#### 10.4.1 Data and Safety Monitoring Board

An NINDS-appointed independent Data and Safety Monitoring Board (DSMB) has been established to monitor the trial. The DSMB is responsible for periodic review of data related to feasibility, safety, and efficacy. A DSMB Charter specifying the composition, responsibilities, frequency, and format of DSMB meetings and the content of DSMB reports has been created and is available to sites.

### 10.4.2 Feasibility

Feasibility of completing the trial and adequately addressing the primary aim will be evaluated by the DSMB at each meeting. While no hard criteria for declaring the trial infeasible are specified, delays in accrual that would preclude adequate enrollment and follow-up within the funding period might be cause for the DSMB to recommend termination of the trial.

#### **10.4.3** Safety

Safety of serum urate elevation will be evaluated by the DSMB at each meeting and at other times as the DSMB may request. Given the diversity of possible adverse event data and the complexities of weighing risks and benefits from treatment, no definitive early stopping criteria for safety are specified. As described in Sec. 5.1.3a, urolithiasis and gouty arthritis are the safety outcomes of greatest concern. If greater than 20% of subjects receiving inosine develop uric acid stones or experience gouty arthritis, then the DSMB might recommend termination of the trial.

## 10.4.4 Blinded Sample Size Re-Estimation

The Steering Committee will review updated estimates of nuisance parameters required for sample size calculation from blinded interim analyses performed using pseudo-randomizations. Interim analyses for possible sample size re-estimation will be performed at the same time as the first planned interim efficacy and futility analysis, i.e., after 2000 person-months of period 1 follow-up are completed, roughly one-third of total anticipated period 1 follow-up. To maintain blinding, pseudo-randomizations stratified by site will be generated to assign pseudo-treatment labels to each participant. This yields a slightly conservative estimate of variance components given that variance attributable to true treatment assignment will remain in the slope and residual terms.

An information-based approach will be used, comparing the square of the observed standard error (SE) for the pseudo-treatment x time interaction term from analysis of the interim data to the square of the SE expected given the observed distribution of follow-up times and the assumptions used for the initial sample size and power calculations. Additional details are provided in the SAP.

A proposal to increase, but not decrease, the sample size will be considered based on the estimated sample size required to achieve 80% power. To avoid the administrative burden of small increases that negligibly affect power, we would not expect to recommend sample size increases of fewer than 30 participants. And recognizing practical constraints, we would not expect to recommend sample size increases of more than 130 participants. The option to decrease sample size is not needed (and can undermine power) because the trial is likely to be stopped early for efficacy or futility if estimates of the true treatment x time interaction are more precise than anticipated. Note that this is an information-based design updating only the nuisance parameters required for power calculations, not an adaptive design updating the planned effect size.

## 10.4.5 Efficacy or Futility

Interim analyses for efficacy or futility will be performed by the unblinded statistician after 2000 and 5000 person-months of period 1 follow-up are completed, roughly one-third and three-quarters of total anticipated period 1 follow-up. Non-binding early stopping for efficacy will be proposed if the active treatment group is superior to placebo for the primary efficacy outcome based on a one-sided p-value of 0.001 or less. Other criteria used in deciding whether to stop early for efficacy will include evaluation of safety and secondary efficacy outcomes. We propose stringent early stopping criteria for efficacy in order to ensure that evidence for efficacy is unambiguous if the study is stopped early. Non-binding early stopping for futility will be proposed based on a beta-spending rule quadratic in information time. If there were no benefit from treatment, then the trial would have a 51% probability of early stopping for futility based on this rule. As with the efficacy evaluation, the decision to stop early for futility will also include

evaluation of feasibility, safety, and secondary efficacy outcomes. Because the efficacy and futility stopping rules are non-binding, we conservatively assume that each look is cumulative for alpha and ignore possible findings of futility when calculating the overall type I error.

#### 10.5 Data Analyses

The following plans describe proposed analyses of all outcomes. A definitive statistical analysis plan (SAP) will be finalized and must be approved by the Steering Committee prior to the final lock of the trial data and breaking of the blind. The final approved SAP may differ in detail from analyses described here.

#### **10.5.1 Primary Analysis**

The primary mITT analysis of rate of change of MDS-UPDRS I-III total scores during period 1 will use a random slopes model with shared baseline. The model will include fixed effects of time, treatment x time, gender, gender x time, an indicator of baseline MAO-B inhibitor use, and baseline MAO-B inhibitor use x time and random site- and subject-specific intercepts and slopes, each with unstructured covariance. Use of a shared baseline adjusts for baseline MDS-UPDRS score $^{245,246}$  in addition to the adjustment for gender and baseline MAO-B inhibitor use. Other baseline covariates, including Smart4SURE participation, may be included in the final model based on review of blinded data and any revision in our understanding of predictors of PD progression prior to finalizing the analysis plan and breaking the blind. Measurements made subsequent to initiating dopaminergic therapy will be censored. Inference of benefit from serum urate elevation will be made by testing whether the treatment x time interaction term is significantly less than zero (i.e., slower progression among subjects randomized to the active arm) using a two-sided test at p < 0.046 for a cumulative two-sided alpha = 0.05.

Our estimate of the effect of serum urate elevation on MDS-UPDRS will be unbiased if observed trajectories are predictive of MDS-UPDRS assessments that are missing due to loss to follow-up or are censored due to initiation of dopaminergic therapy. Data from the SURE-PD trial suggest good conformance of UPDRS I-III total score trajectories to the model assumptions. No non-linearity in treatment effects on observed UPDRS scores was found and models that included quadratic random effects fit worse by Akaike and Bayesian information criteria. Empirical Bayes estimates of 24-month UPDRS scores assuming linear trajectories were all within range of the instrument (range 7.4 to 97.4) even with 85% of the sample being censored prior to the final 24-month observation (median 12 months). Conditional residuals were normally distributed and homoscedastic. Similar assessments and influence statistics will be evaluated in judging the adequacy of the proposed primary analysis in this trial.

## 10.5.2 Alternative Analyses

If analysis of the mITT sample does not indicate benefit of randomization to oral inosine, it is still possible that (a) inosine supplementation is beneficial if the mITT estimates are affected by non-compliance or that (b) serum urate elevation itself is protective if achieved. As a key secondary analyses, we will analyze the AT sample, censoring follow-up after discontinuation of study drug. This will provide an estimate of the effectiveness of inosine among those tolerant of supplementation. We will also analyze the AT sample with substitution of mean increase in serum urate from baseline to week 12 in place of randomized treatment assignment to estimate method-effectiveness of serum urate elevation.

We will further evaluate robustness of estimates from our primary analysis in a number of other secondary analyses, including: (a) alternative models for the mean temporal profile, (b) alternative models for handling observations made after loss to follow-up or initiation of dopaminergic therapy, and (c) alternative models for handling covariance among repeated observations. To relax the assumption of linear change over time, a model with visit and visit x treatment terms in place of the time and time x treatment terms will be fit to permit an unstructured temporal profile. Rather than censoring observations after initiation of dopaminergic therapy, we will consider several models that include all MDS-UPDRS

observations. If participants randomized to inosine initiate dopaminergic therapy at a slower rate than those on placebo, then lower MDS-UPDRS scores at 24 months irrespective of dopaminergic therapy would suggest that the benefit of inosine supplementation carries over after the need for therapy. Alternatively, we will include either a simple time-dependent offset for measurements made in the ON condition or a time-dependent offset equal to the levodopa equivalent dose prescribed at that time. To avoid bias from potentially informative loss to follow-up, we will consider a pattern-mixture model with the fixed effects stratified by length of follow-up. The Combined Assessment of Function and Survival (CAFS) model described in Section 10.5.5 is constructed similarly by comparing pairs of participants over equal lengths of follow-up. To relax the assumption of linear random slopes, a model with a full 12 x 12 unstructured covariance matrix among repeated assessments of MDS-UPDRS (78 covariance terms) will be explored.

## 10.5.3 Subgroup Analyses

The potential for differential benefit from serum urate elevation among subgroups of patients will be tested by including subgroup, subgroup x time, and subgroup x time x treatment interaction terms into the primary random-slopes model. A significant subgroup x time x treatment 3-way interaction in combination with significantly slower progression among members of a subgroup randomized to serum urate elevation vs. members of the same subgroup randomized to placebo will be taken as evidence of differential benefit. The following subgroups will be considered: sex, race (classified as Asian, Black or African American, Caucasian, or other, including multiracial; or as Caucasian vs. non-Caucasian if fewer than 10% of our sample is non-Caucasian), ethnicity (classified as Hispanic or Latino vs. non-Hispanic), use of MAO-B inhibitors at baseline, and age (both categorized as <65 years vs. ≥65 years and continuous).

## 10.5.4 Disability Warranting Dopaminergic Therapy

Treatment differences in time to disability warranting dopaminergic therapy during period 1 will be tested by a Kaplan-Meier logrank test with a two-sided alpha = 0.05. Subjects lost to follow-up will be censored unless available information suggests that a given subject withdrew consent due to increasing disease progression or a desire to seek more aggressive care. Note that subjects will continue to be followed even if they discontinue study drug. As a sensitivity analysis, subjects lost to follow-up will be classified as initiating dopaminergic therapy at the time of their withdrawal.

## 10.5.5 Combined Function and Treatment

A rank-based test of a single outcome combining function as measured by change in MDS-UPDRS I-III total scores and time to disability warranting dopaminergic therapy will be constructed paralleling the CAFS score methodology developed for ALS. MDS-UPDRS I-III total scores will substitute for ALSFRS-R total scores and time to disability warranting dopaminergic therapy will substitute for time to mortality. The test consists of calculating a rank-sum score for each individual relative to pair-wise comparisons with all other subjects. Subjects are ranked according to time to disability warranting dopaminergic therapy when that is observed for both members of a pair or when one is censored after the observed event time for the other. Pairs that cannot be ranked by time to disability warranting dopaminergic therapy are ranked by absolute change from baseline in MDS-UPDRS I-III total score at the maximum follow-up time at which both subjects have an observation. Inference is drawn by calculating a U-statistic from the rank-sum scores.

## 10.5.6 Secondary Efficacy Outcomes

Most secondary efficacy measures will be analyzed using the same shared-baseline, random-slopes model described for analyzing our primary outcome. If analyses of the mITT sample do not indicate significant benefit from serum urate elevation, then the AT sample will be analyzed as well. If important differences

in inference of the primary outcome are drawn from the alternative models described in Sec. 10.5.2, then equivalent models will be explore for our secondary efficacy outcomes.

## 10.5.7 Safety and Tolerability Outcomes

Overall AE and SAE rates will be compared between treatment groups by negative binomial regression. Time to first SAE will be compared between treatment groups by Kaplan-Meier logrank test. The proportion of subjects experiencing (a) each type of AE, classified by MedDRA preferred term and system organ class, (b) clinically-significant abnormal labs, and (c) clinically significant abnormal vital signs, including orthostatic hypotension defined as positional dizziness or other clinical symptoms of orthostatic hypotension or a drop in systolic and diastolic blood pressures of 20 mm Hg and 10 mg Hg or more, respectively, when moving from a supine to a standing position will be compared between treatment groups by Fisher's exact test.

Assuming no administrative censoring, all subjects will be classifiable as tolerant or intolerant, with subjects lost to follow-up or withdrawing consent classified as intolerant. Tolerability will then be estimated by simple proportions tolerant at 12 weeks and 24 months. Serum urate elevation will be declared tolerable at each time point if its exact one-sided lower 95% confidence bound is greater than 50%. If evaluation of tolerance is censored, then Kaplan-Meier product-limit estimates and their complementary log-log confidence bounds will be used. We will explore the relationship between tolerance and use of dopaminergic therapy using Cox regression with use of dopaminergic therapy as a time-dependent covariate.

#### 10.5.8 Symptomatic Effects

The presence of symptomatic effects will be tested using a change-point model constructed as a partial linear spline over time with knots at 12 weeks and 24 months. Both fixed and subject-specific random terms for intercept, slope from baseline to 12 weeks, slope from 12 weeks to 24 months, and slope from 24 to 27 months will be included. Unstructured covariance will be assumed among the random effects (10 terms). The AT sample will be analyzed. Significantly smaller slopes during wash-in or larger slopes during wash-out among subjects treated with inosine using one-sided testing at alpha = 0.025 will be interpreted as symptomatic effects. If symptomatic effects are not found on that basis, the absence of symptomatic effects will be judged based on a non-inferiority test using a non-inferiority bound of 6.3 / 3 = 2.1 points/month in the direction of a symptomatic effect and using one-sided testing at alpha = 0.05.

## 10.5.9 Disease Modification

A three-part test of time to disability warranting dopaminergic therapy will be used to evaluate whether serum urate elevation is disease-modifying $^{247-249}$ . Inference of disease modification would be supported if (a) a Kaplan-Meier logrank test of time to disability warranting dopaminergic therapy during period 1 favors serum urate elevation, (b) the proportion of subjects randomized to serum urate elevation remains significantly lower than placebo at the end of period 2 by Chi-square test, and (c) the time-dependent hazard ratio for time to disability warranting dopaminergic therapy during period 2 is non-inferior to a rate that would lead to equivalence to placebo by 3 months by Cox regression. Inference from each of the three component tests will be evaluated sequentially. Difference in time to disability warranting dopaminergic therapy will be evaluated first. If significant by logrank test with two-tailed alpha = 0.05, then the proportion not yet requiring dopaminergic therapy at the end of period 2 will be tested second. If significant by Chi-square test with two-tailed alpha = 0.05, then non-inferiority of the time-dependent hazard ratio will be tested by Cox regression based on a one-tailed test at alpha = 0.05.

#### 10.5.10 Smart4SURE Substudy

The feasibility of implementing Smart4SURE will be measured by the following metrics among others: (a) proportion of eligible participants who consent to Smart4SURE, (b) proportion of randomized

substudy participants who complete a baseline Smart4SURE assessment, and (c) proportion of randomized substudy participants who complete at least monthly motor and cognitive assessments and quarterly self-report MDS-UPDRS, QoL, and apathy evaluations while on-study in the parent trial.

Correlations between Smart4SURE measures and related clinical assessments will be evaluated both cross-sectionally and longitudinally. Cross-sectional associations will be estimated both by correlation of baseline data and in mixed models using all contemporaneous assessments. The mixed model will regress clinical measures on contemporaneous Smart4SURE measures and will separately estimate within-person and among-person associations by recoding the Smart4SURE measures as person-level trends and deviations from a given participant's trend. Adequacy of the Smart4SURE measures as proxies for clinical assessments requires strong correlation at both within-person and among-person levels. Longitudinal associations will be estimated similarly, with direct correlation of the final period 1 assessments and by similar mixed models of change-scores calculated as the simple differences from baseline.

Exploratory evaluation of Smart4SURE measures as efficacy outcomes will use the same primary, alternative, and subgroup analyses proposed for the primary outcome in Sections 10.5.1-10.5.3 and the same analysis of symptomatic effects specified in Section 10.5.8.

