#### **4.3.3** Consent Procedures

During or before a screening visit, the subject will be thoroughly informed of all aspects of the study, including all scheduled visits and activities, and will be able to ask questions. The subject will be requested to sign and date the informed consent form *prior* to undergoing any study-specific procedures. The original signed and dated informed consent form must be retained by the Investigator in the subject's file and a copy must be provided to the subject. Subjects may also consent to optional substudies: a) blood collection for future biomarker research (see Section 16.2.14), with consent obtained at SC1 at the time of parent trial consent, b) smartphone-based outcomes research (see Section 16.2.15), with consent obtained at SC2 or at any subsequent visit up to and including V09 using an informed consent form separate from

that used for the parent study, and/or c) second DAT neuroimaging to assess change from pre-baseline imaging (see Section 16.2.11.2), with consent obtained at or prior to visit V10.

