#### **6.2.15** Optional Smartphone Outcomes Research Participation

Eligible, consenting subjects may participate in a research substudy designed to assess the feasibility of using smartphone metrics as decentralized assessments of motor and non-motor outcomes of clinical progression in early PD. Self–administered questionnaires and tests are completed by participants using a smartphone application adapted for the SURE-PD3 trial and known as Smart4SURE, as is the substudy. The primary aim of the Smart4SURE substudy is:

• to assess the feasibility of incorporating smartphone application-based outcome measures in phase 3 'disease-modification' trials for people with PD. If feasibility were supported by the substudy results, they may facilitate adoption of smartphone metrics as secondary or eventually primary outcomes in future neurotherapeutics trials for PD.

Key secondary aims of the substudy are:

- to correlate the cross-sectional assessments and the longitudinal changes documented by smartphone sensors and questionnaires with related elements of SURE-PD3's primary (MDS-UPDRS) and secondary outcome measures.
- to compare rates of change in motor performance and in cognitive and other non-motor functions among substudy participants randomized to inosine versus placebo (i.e., an exploratory test of the parent study's central hypothesis for these novel measures).

without interfering with the parent project's goals. Substudy participation is voluntary. After subject training at the 2nd screening visit (SC2), or if necessary at a subsequent visit, smartphone assessments will be conducted off-site at each participating subject's convenience. Accordingly Smart4SURE is not expected to appreciably increase burden to subjects or site staff during regular study visits, nor to compromise the clinical assessments conducted during visits. Serial assessments for Smart4SURE consist primarily of:

- Activity Sessions comprising ~15 minutes of motor and cognitive tests (including finger tapping, voice, tremor, gait and memory) to be conducted at least monthly but no more frequently than weekly. At least one activity session should be completed prior to the baseline visit for subjects who consented prior to their baseline visit.

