## Summary and Justification of SURE-PD3 protocol revisions from version 3.0 to 4.0 (11/28/17)

#	Proposed Change	Section	Purpose
1	Addition of an optional serial DAT scan substudy which involves a second DAT scan one to two months following a subject's two-year study visit	6.2.11.2, 7.1.8 - 7.2.12, 7.3.1, 10.5.11	To allow for comparative analysis between pre- and post-study drug DAT scan measurements
2	Clarifying language concerning the DAT scan eligibility read process	6.2.11.1	To clarify the process used by the imaging core in determining eligibility
3	Clarifying that the projected enrollment number of 270 is an approximation (where not already indicated)	Synopsis, 3.1, 4.0	To unify the description of the study enrollment goal
4	Reduction in number of consecutive urine pH values ≤5.5 needed to initiate alkalinization therapy from 4 to 3	8.4.2	To lower the threshold for initiating alkalinization treatment to reduce the risk of uric acid kidney stones in those most at risk
5	Expansion of Smart4SURE sub-study enrollment	7.1.8 – 7.2.11	To allow subjects who have passed their baseline visit to enroll in the sub-study
6	Updating Schedule of Activities chart to include above-mentioned changes as well as unplanned visits	7.7	To improve clarity
8	Minor revisions	Throughout	To improve clarity

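### Smart4SURE metric (b), and possibly metric (c), in Protocol 10.5.10 keeps post-baseline joiners in the denominator for sessions they could not have done

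*Protocol*

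**What the plan says.** Protocol 6.2.15 states the primary aim of Smart4SURE: "to assess the feasibility of incorporating smartphone application-based outcome measures in phase 3" disease-modification trials.

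Protocol 10.5.10 lists three feasibility metrics and notes that there may be others:

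- Metric (a) is the "proportion of eligible participants who consent to Smart4SURE".
- Metric (b) and the first half of metric (c) share one denominator, everyone in the substudy who was randomized: "substudy participants who complete a baseline Smart4SURE assessment, and (c) proportion of randomized substudy participants who complete at least monthly motor and cognitive assessments".
- The second half of metric (c) adds the surveys and the time frame: "quarterly self-report MDS-UPDRS, QoL, and apathy evaluations while on-study in the parent trial".

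Protocol 4.3.3 sets the substudy consent window: "with consent obtained at SC2 or at any subsequent visit up to and including V09". V09 is the month 21 visit. The visit lists in 7.1.8 to 7.2.11 and the Schedule of Activities agree. The summary of changes to version 4.0 gives the purpose: "To allow subjects who have passed their baseline visit to enroll in the sub-study".

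Protocol 6.2.15 makes the early session conditional on when the person consented: "At least one activity session should be completed prior to the baseline visit for subjects who consented prior to their baseline visit". It places the same condition on the first survey.

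The SAP defines no Smart4SURE feasibility metric. Its Introduction leaves ancillary studies to ancillary SAPs where they are not covered, and SAP 4.3 and 5.17 name the smartphone measures only as exploratory endpoints and assessments.

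**The concern.** The conduct sections and the analysis section do not match. Section 6.2.15 asks for a pre-baseline session only from people who had consented by then. Section 10.5.10 scores that assessment over every randomized substudy participant, whenever they joined. Someone who consents at month 9 is in the denominator of (b) and can never be in its numerator.

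Metric (c) may have the same problem. Its window is tied to time on the parent trial, and nothing says that the monthly and quarterly counts begin at substudy consent.

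At stake is how the substudy's primary aim is read. Section 6.2.15 says that favourable results may help smartphone measures to be adopted as outcomes in later trials. A proportion lowered by the date people were allowed to join would be taken for poor adherence. Two analysts could also report different values of (c) from the same data.

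**Working it through.** The documents give no feasibility target, expected proportion or substudy sample size, so there is no stated figure to reproduce.

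**Metric (b).** Let s be the share of randomized substudy participants who consent after the baseline visit, and p the completion rate among those who consented at or before it. Neither is given in the documents; both are assumed here. With baseline read as the trial baseline, no one in the share s can have a baseline assessment, so

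(b) as written = (1 - s) x p + s x 0 = (1 - s) x p.

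| s (assumed) | p = 100% (ceiling) | p = 90% | p = 80% | Restricted denominator |
|---|---|---|---|---|
| 10% | 90% | 81% | 72% | p |
| 20% | 80% | 72% | 64% | p |
| 30% | 70% | 63% | 56% | p |
| 50% | 50% | 45% | 40% | p |

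The relative loss is s, whatever p is. With the denominator limited to those who consented at or before the baseline visit, the metric returns p in every row.

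**Metric (c), window starting at trial baseline.** A participant who joins at month m of T on-study months can cover at most (T - m)/T of them. T is 24 months to the end of treatment, or 27 to the Safety Visit.

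| Joins at month m | T = 27 | T = 24 |
|---|---|---|
| 6 | 21/27 = 78% | 18/24 = 75% |
| 12 | 15/27 = 56% | 12/24 = 50% |
| 21 | 6/27 = 22% | 3/24 = 12.5% |

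Because (c) counts people with at least monthly completion, each of these participants would be a non-completer however faithful they were after joining. The share affected is slightly smaller than s, since someone who consents at V01 (week 3) can still fit a session into the first month.

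**Metric (c), window starting at substudy consent.** A fully adherent late joiner is a completer and there is no dilution.

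**Metric (a).** Late consenters add to the numerator. A longer consent window cannot lower this proportion for a given set of eligible participants.

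**The case against.** - **Definitions may sit elsewhere.** The opening of Protocol 10.5 calls its analyses proposed and allows the final SAP to differ in detail, the SAP defers ancillary studies to ancillary SAPs, and the metric list is open-ended. An ancillary SAP not among these documents could set the denominators. This stands as a limit on certainty. But 10.5.10 is the only definition in the documents, and additional metrics would not correct the named ones.
- **Baseline could mean a person's first app session.** That would remove the problem in (b). The text does not say so: 6.2.15 ties the early session to the baseline visit, and 10.5.10 uses baseline elsewhere, for correlations and change scores, without redefining it. Trial baseline is the natural reading.
- **The on-study phrase in (c) may only close the window.** It can fairly be read as excluding lapses after a person leaves the trial, and no smartphone activity is scheduled before someone joins. This objection largely stands: (c) is ambiguous rather than plainly wrong. A reader might infer that a fully adherent person who joins at month 12 is certain to fail (c); the wording does not settle that.
- **Consent at the baseline visit is a borderline case.** Section 7.1.8 allows consent and app training at that visit, so a same-day session is possible. Limiting (b) to those who consented strictly before baseline would wrongly exclude these people.

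**Conclusion.** The point holds for metric (b), provided that baseline means the trial baseline and that no ancillary SAP redefines the denominator. The direction is then certain for any s above zero. The size is not known, because the documents do not give s; an assumed 10% to 50% puts the ceiling at 90% to 50%. For metric (c) the point is conditional on the window opening at trial baseline.

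A reader might go further and infer that Smart4SURE feasibility as a whole is understated, or that the substudy would be wrongly judged infeasible. The documents support neither. Metric (a) is not lowered, no threshold or decision rule exists for a low proportion to trip, and section 6.2.15 speaks only of results that may facilitate adoption. Smart4SURE is an optional substudy, and these feasibility denominators do not enter the parent trial's efficacy or safety analyses. This is a minor wording correction, worth making because it concerns the substudy's primary aim.

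**What to change.** In Protocol 10.5.10 or the ancillary SAP:

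1. Limit metric (b) to participants who consented to the substudy at or before the baseline visit, and state that a same-day session counts for those who consented at that visit.
2. For metric (c), count the monthly and quarterly sessions from each participant's substudy consent to the end of their participation in the parent trial.
3. Report early and late joiners separately.

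The cost is a few lines of text. Substudy consent dates and app session dates come from the planned procedures, so no new data are needed.
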